#### 2.5.2. INTERVENTION GROUPS

#### 2.5.2.1. GROUP A ATM (FM)

ATM involve a series of structured verbally guided motor activities usually conducted in the form of group lesson sessions. The lessons are based on the developmental sequence and vary in the level of difficulty from relatively complex, applied to people with physical impairments to hypercomplex addressed to those with high motor requirements. The duration of each lesson varies between 30-60 minutes. In the beginning, simple, comfortable, gentle movements are performed that will gradually develop into complex ones, with a self-determined manner and rhythm by the trainee. The purpose is the teaching of execution rather than the completion of the movement. The improvement of awareness and the organization of the body is caused through the verbal instructions-orders or questions-problems that is posed by the educators of the method. The above aims at implementing a sequence of movements and focusing on different parts of the body (internal feedback). A corollary to this is the empathy of basic functions. Each lesson that will

be included in the protocol of the ATM group, will have a specific request and topic, while it will be organized around a functional activity.

ATM affects muscle tone, reduces tension and unnecessary effort, aiming at improving the sensorimotor perception. The latter induces the absolute regulation of movements by the trainees. Among the goals is to increase awareness regarding the mechanics of movements. Through the technique, the suspension of stereotyped movement patterns, the expansion of movement options, the learning of new movements and the presentation of a new way of composing them are attempted. A crucial role for the achievement of the aforementioned is played by the reduction of mental tension, which is caused by encouraging less effort to be exerted each time during the movement. Correcting incorrect moves goes against the philosophy of the method that supports inquiry learning.

According to the philosophy of FM, the treatment of chronic neck pain requires an approach from the perspective of other components besides the cervical spine. In this light, neck pain can originate from the neck but also from other causes, including inadequate breathing patterns, pelvic tilts, insufficient differentiation of eye or head movements, overuse of the upper extremity musculature. An inseparable relationship is detected between the neck and the temporomandibular joint, i.e. the incorrect position of the former affects the function of the latter and conversely the increased tension in the temporomandibular joint changes the muscle tone of the neck. This category also includes the limited movement of the lumbar spine as well as the injury of the end of the foot that disrupts the smooth functioning of the biokinetic chain (Plastaras *et al.*, 2011).

In the A ATM group (intervention group) the ATM technique will be applied in group sessions (6-8 patients) by a physiotherapist, specialized in the FM with at least five years of experience. The ATM protocol will be implemented in ten sessions, two per week, of 50 minutes each, for a period of 5 weeks.

On the remaining days, home exercises will be given to the patients in the form of printed illustrated instructions for their correct execution. These ATM exercises, will be a repetition of the ATM lesson that they will have been taught and, will be performed once a day, until the next session, where participants will learn and implement the next ATM lesson. The execution rate of the movements and the movement pattern will be individualized, as they dependent on each patient.

In this protocol ten ATM-sessions will be conducted, which are derived from original courses taught by Moshe Feldenkrais and each of them will address a specific function within the developmental repertoire. In details, the first, "Rolling the fists", will aim at the connection between upper limbs and spine. The second, "Stomach and chest first" will activate the diaphragm. The third, "Hip and Shoulder Integration" is the first approach to shoulder differentiation. The "The Movement of the Eyes Organizes the Movement of the Body" helps control the functional connections between the eyes and neck muscles. The "Skewering the spine in the chest" will promote the movement of the spinal chain and is a continuation of the logical choice of "Rolling the fists" with the difference that it aims at the greater range of activation of the central point of the body, connecting the trunk with the upper limbs. The «On the back; twisting the spine with the head fixed» will improve rotation by changing the relationship between the proximal (below the A7 vertebra) and distal cervical spine parts of the spine. The "A clock in front of the face" will enhance the shoulder-head and spine differentiation. The "Breathing (To weld by breathing)" will increase the volume and flexibility of the rib cage. The «Edges of the feet» will help to the connection of the ankle joints with the hip joints and through them with the spine and head. Finally, the "On the side, the sternum becoming flexible" will mobilize the sternum in order to improve the rotation and extension of the neck. The above lessons have been translated and modified by the main researcher following a specific format as a methodological aid for their reading and understanding.

Below is a summary table of the ATM courses in the order they will be held (Table 3).

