# 2.3. RESEARCH HYPOTHESISES

Two main research questions are formulated regarding the effectiveness of ATM versus a standard treatment regimen consisting of acupuncture and stretching, but also the effectiveness of ATM as monotherapy, which will be investigated through appropriate statistical controls. The formal basis of statistical tests is the null hypothesis under which there is no association between the exposure and the outcome (Killeen, 2005). Starting from the assumption of no relationship, statistical tests quantify the probability that the observed relationship was observed by chance, due to the random sampling distribution. When the null hypothesis cannot be rejected then the observed relationship is attributable to chance rather than a true effect of the exposure on the outcome (Banerjee *et al.*, 2009).

Thus, the null hypotheses to be tested are formulated as follows:

- Research question 1: Effectiveness of ATM (intervention group before the intervention vs. the same group after the intervention)
  - Null hypothesis H0A1: The application of ATM does not affect the pain sensitivity assessed by the Pain Pressure Threshold (PPT) measured

with the pressure algometer (Commander Algometer) in patients with chronic neck pain (main hypothesis).

- Null hypothesis H0A2: The application of ATM does not affect the cervical range of motion (ROM) recorded with the Moover threedimensional (3D) Inertial Motion sensor in patients with chronic neck pain (secondary hypothesis).
- Null hypothesis H0A3: The application of ATM does not affect the strength of deep neck flexor muscles as measured by the Chattanooga Stabilizer Pressure Biofeedback in patients with chronic pain in the cervical spine (secondary hypothesis).
- Null hypothesis H0A4: The application of ATM does not affect the respiratory function assessed by the portable spirometer (MIR Spirodoc) in patients with chronic neck pain (secondary hypothesis).
- Null hypothesis H0A5: The application of ATM does not affect the pain in the cervical spine in terms of its intensity and quality, i.e., its sensory, emotional and behavioral dimensions using the McGill Pain Questionnaire-short form (SFMPQ) in patients with chronic neck pain (secondary hypothesis).

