# 2.5. MATERIAL AND METHOD

## 2.5.1. SAMPLE

## 2.5.1.1. SAMPLE CHARACTERISTICS

During the initial calculation of the sample number, the number of the participants was determined, with purpose, the method of Analysis of Variance (ANOVA) in two groups of equal population, to identify a standardized effect size equal to 0.25 with a power of 80% and a level of statistical significance of 5%. The standardized effect size is defined as follows: Let the measurement tool X and groups A, B and  $\mu$ A,  $\mu$ B

be the mean values of X in groups A and B. SD is the Standard Deviation of X in the whole population. The effect size is given by the formula  $(|\mu A-\mu B|)/SD$ . The calculation was performed with the program G\*power version 3.1.9.7\* and the necessary sample size was calculated at 126 subjects. According to the relevant literature, similar standardized sample sizes have been used in two studies dealing with chronic neck pain (Lundblad *et al.*, 1999; Malmgren-Olsson *et al.*, 2009). Moreover, a dropout rate of 20% was expected, so a final number of around 152 patients is realistic for this study.

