#### 6.5.2.2. GROUP B A-S

In the B A-S group (active control group) before the implementation of the A-S protocol, a complete musculoskeletal assessment of the patients by an experienced physiotherapist trained in the identification of MTrPs, will be applied. The MTrP identification will be achieved by palpation of the muscles under examination (upper trapezius, levator scapulae, splenius capitis and cervicis), according to the criteria of Travell and Simons (1992). The points identified will be marked with indelible ink and recorded on a pain diagram. The patients' skin will be cleaned with alcohol before the acupuncture.

The A-S protocol will be performed in ten individual sessions, two per week, of 40 minutes each, for a period of 5 weeks. Acupuncture will be performed for 25 minutes by an experienced and licensed physiotherapist. It will include the insertion of a sterile disposable needle of 0.25 mm diameter and 25 mm length (DongBang Acupuncture, Inc., Korea) into standardized as possible appropriate local, regional and general points, that will modify the behavior of the pain in the area of the Cervical Spine.

Local acupoints will include:

- Small Intestine 14 (SI 14) which is located 3 Cun (1 Cun = maximum width of the patient's thumb) lateral to the lower border of the spinous process of the first thoracic vertebra (T1) (Sun *et al.*, 2019) and is a common MTrP in the levator scapulae muscle.
- Gallbladder 21 (GB 21) which is located at the midpoint of the line connecting the acromion with the spinous process of the seventh cervical vertebra (A7) (Wilke *et al.*, 2014; Sun *et al.*, 2019) and is a common MTrP in the upper trapezius muscle.
- Gallbladder 20 (GB 20) which is below the occipital, in the depression between the insertions of the sternocleidomastoid and the trapezius muscles (Wilke *et al.*, 2014; Sun *et al.*, 2019).
- Bladder 43 (BL 43) which is located at the same height with the upper limit of the spinous process of the fourth thoracic vertebra (T4), 3 Cun lateral to the midline (Wilke *et al.*, 2014).

Regional acupoints will include:

- Huato Jiaji C5 which is located paraspinal at the level of the fifth cervical vertebra (A5).

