# 2.9. STATISTICAL ANALYSIS

Quantitative variables will be expressed as mean and standard deviation (SD). Qualitative variables will be expressed as absolute (N) and relative (%) frequencies. Pearson's  $\chi^2$  test and Fisher's exact test (where it is necessary) will be used to compare proportions, as well as McNemar test will be used to compare the percentages of kinesiophobia between measurements. Student's t-test or nonparametric criterion Mann-Whitney will be used for the comparison of the quantitative variables between the two groups. The change in the used scales and other indicators of the participants over time will be tested using linear mixed models from which dependence coefficients ( $\beta$ ) and their Standard Errors (SE) will be obtained. The group, the measurement (endline vs baseline) and their interaction term (to be tested in which extent the change is different between measurements in the two groups), will be introduced as independent variables. In the cases, where the interaction term will be found significant, sex, age, BMI and the symptoms duration will be introduced in the model (the chosen confounding factors are the most significant), in order to be tested if the interaction remain significant. Moreover, in the case that measurements at some outcome measures will be found to differ significantly at the initial measurement between the two groups, a result not due to systematic error but found to be due to random sampling. In these cases, their initial values will be entered into the mixed linear models as an independent variable to ensure that the findings from the models are not due to the initial differences between the groups. In cases that will be found significant differences between baseline measurements, between the two groups, the initial measurements will be introduced in linear mixed models as independent variable, in order to be ensured that the findings from these models are not due to initial differences between the groups. All reported p values will be two-tailed and statistical significance will be set at p < 0.05. Analyses will be conducted using the IBM SPSS Statistics 26.0.

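### ATM is taught in classes of 6-8 and A-S is given individually, but section 2.9 has no class term; if change correlates within classes, the standard errors are too small, mainly for the within-ATM question

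*Combined protocol and SAP*

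**What the plan says.** Delivery differs by arm. In section 2.5.2.1, "the ATM technique will be applied in group sessions (6-8 patients) by a physiotherapist", for ten sessions over five weeks. Each session is the one "where participants will learn and implement the next ATM lesson". Section 6.5.2.2 says: "The A-S protocol will be performed in ten individual sessions".

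Section 2.9 states: "The change in the used scales and other indicators of the participants over time will be tested using linear mixed models". The listed independent variables are "The group, the measurement (endline vs baseline) and their interaction term". Sex, age, BMI and symptom duration are added if the interaction is significant, and baseline values are added if the arms differ at baseline. No random effect, covariance structure, class identifier or cluster-robust standard error is named. The same section also plans t-tests or Mann-Whitney tests between the groups.

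Section 2.5.1.1 sizes the trial for "the method of Analysis of Variance (ANOVA) in two groups of equal population", with no ICC or design effect. Section 2.3 has two research questions, each with a main hypothesis on PPT. The first is a within-arm comparison, "intervention group before the intervention vs. the same group after the intervention". The second compares ATM with A-S.

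**The concern.** Patients who share a class share companions, time of day, calendar period and the way each lesson went. If this makes their changes alike, the ATM arm holds less independent information than its head count suggests. A patient random effect links one patient's two measurements. It does not link the changes of different patients in the same class, so it cannot absorb this correlation.

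Both main hypotheses use the ATM arm. The within-ATM test takes the full effect because all its patients are in classes. The randomised comparison takes roughly half, because only one of its arms is grouped. The risk is a nominal 5% test that rejects too often and intervals that are too narrow. If class membership is not recorded, the trial can neither correct for this nor show that it is negligible.

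**Working it through.** **The plan's own figure.** Section 2.5.1.1 gives 126 patients for effect size 0.25, 80% power and 5% alpha. With independent patients and 0.25 read as Cohen's f (a mean difference of 0.5 SD), n per arm = 2 × (1.96 + 0.842)² / 0.5² = 62.8, so 63 per arm and 126 in total. The figure therefore contains no allowance for classes. (Under the definition written in 2.5.1.1, a mean difference of 0.25 SD, the total would be 504. That is a separate matter.)

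**Inputs.**
- Class size m is 6-8 (2.5.2.1); 7 is used below.
- There are 76 patients per arm (2.5.1.2). Eleven classes of 7 make 77, close to 76.
- The test is two-sided at 0.05 (2.9).
- Assumed: the ICC, meaning the share of the variance of ATM change due to class, at 0, 0.01, 0.05 and 0.10; stable classes; a patient random effect in the model.

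**Formulas.** Set the variance of change in ATM to 1. The mean ATM change then has its variance multiplied by 1 + (m − 1) × ICC = 1 + 6 × ICC. Only ATM carries class variance, so change in A-S has variance 1 − ICC. A mixed model with a patient effect and a common residual variance pools the two, giving about 1 − ICC/2. The ratios of true to estimated variance are:
- within ATM: (1 + 6 × ICC) / (1 − ICC/2)
- ATM versus A-S: (2 + 5 × ICC) / (2 − ICC)

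Actual alpha = 2 × [1 − Φ(1.96 / √ratio)].

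| ICC | Ratio, within ATM | Alpha | Ratio, ATM vs A-S | Alpha |
|---|---|---|---|---|
| 0 | 1.000 | 5.0% | 1.000 | 5.0% |
| 0.01 | 1.065 | 5.8% | 1.030 | 5.3% |
| 0.05 | 1.333 | 9.0% | 1.154 | 6.8% |
| 0.10 | 1.684 | 13.1% | 1.316 | 8.8% |

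Simulation of the patient-effect mixed model (two time points, 11 classes of 7, 76 A-S patients, 100,000 runs per cell, pre-post correlation 0.5 and 0.8) gave 5.0-5.1 / 5.7-5.8 / 9.0-9.1 / 13.0-13.1% within ATM and 5.0-5.1 / 5.2-5.3 / 6.8-6.9 / 8.7-8.8% between arms.

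A simpler formula that gives both arms the same total variance, with ratios 1 + 6 × ICC and 1 + 3 × ICC, yields 5.7 / 8.6 / 12.1% and 5.3 / 6.8 / 8.6% at ICC 0.01 / 0.05 / 0.10. It slightly understates the problem for the planned model, but it shows the sensitivity to class size. Over m = 6 to 8 it gives 5.6-5.8 / 8.0-9.2 / 11.0-13.3% within ATM and 5.3-5.4 / 6.5-7.1 / 8.0-9.2% between arms.

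**If no patient effect were fitted.** At ICC 0 and pre-post correlation r, the estimated variance of change would be too large, with ratio 1 − r. At r = 0.5, alpha = 2 × [1 − Φ(1.96 / √0.5)] = 0.6%. At r = 0.8 it is about 0%. The error then runs in the opposite direction.

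**An analysis that holds its level.** A test on class-mean changes with class-level degrees of freedom gave 4.9-5.1% in every simulated cell, including unequal classes and 20% dropout. A mixed model with a class variance bounded at zero was conservative at low ICC: within-ATM alpha was 3.5-3.6% at ICC 0, where the class variance was estimated as zero in about 55% of runs.

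**The case against.** The strongest objection is that the size is wholly assumed. No ICC is given and nothing says that classes keep the same members. Recruitment runs on from July 2022 until the target is met (2.5.1.4), which could mix classes. Much of the design also favours a low ICC. There appears to be one ATM provider (2.5.1.2), there is one ATM venue (2.5.1.3), and everyone receives the same ten lessons and practises daily at home. Moreover, "The execution rate of the movements and the movement pattern will be individualized". At ICC 0.01 nothing of practical importance is lost. The largest inflation also falls on an uncontrolled before-after test, which is the weaker of the two questions.

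All of this stands, and it limits the point to a conditional one. It does not remove it: the fixed lesson order makes stable classes plausible, and time of day, calendar period and class composition still differ between classes.

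A reader might also infer that section 2.9, by naming no random effect at all, makes the standard errors smaller still. That is wrong. Leaving out the patient effect would make the tests of change far too cautious. Linear mixed models for change over time are most naturally read as including one, so its absence from the text is a reporting gap rather than a second source of inflation.

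**Conclusion.** The point holds in conditional form. The partial nesting and the absence of any class term are plain in the documents. Given a patient random effect, stable classes and a positive ICC, the planned standard errors are too small. Alpha is then about 9% within ATM and 6.8% between arms at ICC 0.05, and about 13% and 8.8% at 0.10. At 0.01 the effect is negligible. At 0, with the patient effect fitted, the planned tests are correct. The t-test and Mann-Whitney comparisons in 2.9 ignore class in the same way.

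A reader might infer that the trial's type I error is known to be inflated, or that the sample size must be raised. The documents support neither, because they give no ICC. What they support is a cheap safeguard: worth making, with medium confidence about how much it will matter.

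**What to change.** 1. Record each ATM patient's class and any change of class.
2. State the patient random effect in section 2.9.
3. For both main PPT hypotheses, pre-specify one named sensitivity analysis on ATM class-mean changes with class-level degrees of freedom. For ATM versus A-S, compare class means with individual A-S changes using Satterthwaite degrees of freedom. Require a positive claim to be qualified if it does not hold there.
4. Report the estimated class ICC, noting that about 11 classes estimate it poorly.
5. State in 2.5.1.1 that the sample size assumes no class clustering.

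The cost is one data field and one extra analysis. At ICC 0 its within-ATM interval is wider by t(10) / t(75) = 2.228 / 1.992, about 12%. The between-arm interval is wider by t(35.3) / t(150) = 2.029 / 1.976, about 3%. The analysis is only approximate if patients change class. It does not remove the confounding of provider with arm (2.5.1.2 appears to give each arm a single provider), which should be stated as a limitation. Nor does it turn the within-ATM test into a controlled comparison.

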# Table 3. Awareness Through Movement (ATM) Lessons

#### 1°: Rolling the fists

Source: ATM Lesson from Alexander Yanai #68 (Feldenkrais 1995a)

#### 2°: Stomach and chest first

Source: ATM Lesson from Alexander Yanai #35 (Feldenkrais 1995b)

#### 3°: Hip and Shoulder Integration

Source: San Francisco Evening Class, Volume 1, Lesson 7 (Feldenkrais 1980)

# 4°: The Movement of the Eyes Organizes the Movement of the Body

Source: Lesson 10 from ATM Book (Feldenkrais 1990)

#### 5°: Skewering the spine in the chest

Source: ATM Lesson from Alexander Yanai Lesson #308 (Feldenkrais 2000)

#### 6°: On the back; twisting the spine with the head fixed

Source: ATM Lesson from Alexander Yanai #110 (Feldenkrais 1995c)

#### 7°: A clock in front of the face

Source: ATM Lessons from Alexander Yanai #82 (Feldenkrais 1995d)

#### 8°: Breathing (To weld by breathing)

Source: ATM Lesson from Alexander Yanai #179 (Feldenkrais 1997a)

#### 9°: Edges of the feet

Source: ATM Lesson from Alexander Yanai #433 (Feldenkrais, 2001)

#### 10°: On the side, the sternum becoming flexible

Source: ATM Lesson from Alexander Yanai #217 (Feldenkrais 1997b)

#### 6.5.2.2. GROUP B A-S

In the B A-S group (active control group) before the implementation of the A-S protocol, a complete musculoskeletal assessment of the patients by an experienced physiotherapist trained in the identification of MTrPs, will be applied. The MTrP identification will be achieved by palpation of the muscles under examination (upper trapezius, levator scapulae, splenius capitis and cervicis), according to the criteria of Travell and Simons (1992). The points identified will be marked with indelible ink and recorded on a pain diagram. The patients' skin will be cleaned with alcohol before the acupuncture.

The A-S protocol will be performed in ten individual sessions, two per week, of 40 minutes each, for a period of 5 weeks. Acupuncture will be performed for 25 minutes by an experienced and licensed physiotherapist. It will include the insertion of a sterile disposable needle of 0.25 mm diameter and 25 mm length (DongBang Acupuncture, Inc., Korea) into standardized as possible appropriate local, regional and general points, that will modify the behavior of the pain in the area of the Cervical Spine.

Local acupoints will include:

- Small Intestine 14 (SI 14) which is located 3 Cun (1 Cun = maximum width of the patient's thumb) lateral to the lower border of the spinous process of the first thoracic vertebra (T1) (Sun *et al.*, 2019) and is a common MTrP in the levator scapulae muscle.
- Gallbladder 21 (GB 21) which is located at the midpoint of the line connecting the acromion with the spinous process of the seventh cervical vertebra (A7) (Wilke *et al.*, 2014; Sun *et al.*, 2019) and is a common MTrP in the upper trapezius muscle.
- Gallbladder 20 (GB 20) which is below the occipital, in the depression between the insertions of the sternocleidomastoid and the trapezius muscles (Wilke *et al.*, 2014; Sun *et al.*, 2019).
- Bladder 43 (BL 43) which is located at the same height with the upper limit of the spinous process of the fourth thoracic vertebra (T4), 3 Cun lateral to the midline (Wilke *et al.*, 2014).

Regional acupoints will include:

- Huato Jiaji C5 which is located paraspinal at the level of the fifth cervical vertebra (A5).
- Bladder 10 (BL 10) which is located on the horizontal line, passing between the spinous processes of the first (A1) and the second (A2) cervical vertebra and the oblique line, passing through the outer limit of the upper trapezius muscle, 1.3 Cun bilaterally of the vertical axis of the body, passing through the spinous processes of A1-A2 (Wilke *et al.*, 2014; Sun *et al.*, 2019).
- Governing Vessel 14 (GV 14) in the depression, inferior to the spinous process of the seventh cervical vertebra (A7) (Karavis, 2011; Wilke *et al.*, 2014).

General acupoints will include:

- Triple Energizer 5 (TE 5) which is located 3 cm above the joint line of the wrist, at the dorsal surface of the forearm between the radius and ulna (Wilke *et al.*,2014; Calamita *et al.*, 2018)
- Large Intestine 4 (LI 4) in the hollow of the radial side of the hand, approximately at the midpoint of the 2nd metacarpal.

After the needle will be removed, firm compression will be applied to the injection sites for 40 seconds to prevent any microbleeding (Campa - Moran *et al.*, 2015). The protocol acupoints are listed in Table 4.

Local	Regional	General
SI 14 (MTrP in the levator	Huato Jiaji C5	TE 5
scapula muscle)	BL 10	LI 4
GB 21 (MTrP in the upper	GV 14	
trapezius muscle)		
GB 20		
BL 43		

Potential events, except for dermatitis, will be managed in accordance with the "Management of Adverse Reactions to Acupuncture and Dry Needling" section of the Guide to Safe Acupuncture and Use of dry needling of the World Confederation of Physical Therapy (WCPT) and the special subgroup dealing with acupuncture (International Acupuncture Association of Physical Therapists – IAAPT). In the event of dermatitis after the application of acupuncture, a wet towel or cloth can be applied to the affected area, followed by a cream or ointment containing calcineurin inhibitors or a corticosteroid cream, gel or ointment. The affected skin can be subjected to phototherapy, i.e., controlled amounts of natural or artificial light (Dermatitis, 2020). If symptoms persist, the patient should be referred to their treating physician. It is pointed out that the side effects result from improper sterilization and use of the needles (Sfara, 2013). White (2004) estimated the risk of a serious adverse event to be 0.05/10.000 treatments and 0.55/10.000 patients.

The 15-minute stretching will also follow a pre-planned application and explanation process and will be as systematic as possible for patients. They will be performed at home, once a day, after prior instruction by the same physical therapist. Stretching will be applied to the following muscles: upper trapezius, levator scapulae, scalene, cervical extensors (splenius, spinalis, semispinalis, longissimus capitis and cervicis, iliocostalis cervicis, multifidi and suboccipital), and sternocleidomastoid. According to Häkinnen et al., the duration of each stretch will be 30 seconds and will be repeated three times (Häkkinen *et al.*, 2007), with one minute rest in between sets and ten seconds rest between each try.

